## **2.2 Study Design and Procedures**

### **2.2.1 Study Design**

This is an unblinded two-arm, multi-site, prospective, randomized controlled pilot trial comparing the effectiveness of the PILOT intervention with TAU on the frequency of self-reported overdose risk behaviors for those who survive a NFOO and present to the ED.

A total of approximately 150 eligible patients will be randomized (approximately 50 per each of 3 sites) in a 1:1 ratio to either TAU or PILOT over 12 months of recruitment. Participants will be engaged in the study for up to 210 days (7 months), which will include 180 days (6 months) of active intervention (PILOT) or TAU, and a 210-day follow-up assessment after the completion of the intervention.

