## **2.2.4 Randomization**

Following the collection of the assessments required for screening and eligibility, eligible participants will be randomized in a 1:1 ratio to PILOT or TAU. The randomization procedure will be conducted electronically by the DSC using a permuted block design with random block sizes and stratified by site and homelessness status. A separate randomization plan will contain additional details regarding treatment allocation.

A DSC statistician will review the randomization data on a regular basis to ensure that the scheme is being implemented according to plan. If a participant drops out of the study at any point after randomization, the randomization slot will not be re-allocated to a new participant due to the original intent-to-treat nature of the study.

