## 7.8 Analyses of the Exploratory Outcome Measures

The following are the planned statistical analysis methods for the specified exploratory objectives. However, given the exploratory nature of these, the actual analysis methods may differ from the proposed methods given below.

1. Each step on the modified SUD Cascade of Care will be treated as a binary outcome. A separate logistic regression model will be fit to each with at least a treatment covariate. The effect of PILOT as compared to TAU will be measured by an odds ratio (OR). The OR will be reported, along with 95% confidence interval and p-value, for each step. This process will be repeated for the 30-, 90-, and 180-day outcomes.
2. Initiation for medications for OUD in the ED, among those participants with OUD, will be summarized by frequencies and percentages in each treatment arm. The effect of PILOT compared to TAU will be measured by an OR with 95% confidence interval. A Chi-squared test will be performed.
3. Number of days of self-reported frequency of use in the past 7 days will be summarized by treatment arm. A hypothesis test analogous to the primary outcome will be conducted.
4. The number of meaningful contacts with a PILOT peer in the past month will be summarized by treatment arm. Similar to the primary outcome, the effect will be measured by a RR with 95% confidence interval. A hypothesis test analogous to the primary outcome will be conducted.
5. Self-reported attendance in a 12-step meeting, peer support services, other recognized recovery organization, or formal SUD treatment at any time during study participation will be summarized by frequency and percentages in each treatment arm. The effect of PILOT as compared to TAU will be measured by an OR with 95% confidence interval. A Chi-squared test will be performed.
6. The percent of urine toxicology screens positive for primary substance of use will be summarized by proportion greater than 0% and continuous descriptive statistics for the proportion positive by treatment arm.
7. Occurrence of a non-fatal overdose at any time during study participations will be summarized by frequencies and percentages. The effect of PILOT as compared to TAU will be measured by an OR with 95% confidence interval. A Chi-squared test will be

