performed. The same process will be done for all-cause mortality and death by overdose. In the event of likely dropout, time-to-event analyses may need to be performed instead. In such cases, simple Kaplan-Meier plots will be given with associated log-rank tests on the effect of PILOT as compared to TAU. Cox proportional hazards regression models may be considered as well. All-cause mortality or death by overdose may present a competing risk for non-fatal overdose. Causes of death different from overdose (that is, those with an all-cause mortality that are not overdose) may present a competing risk for death by overdose as well. As such, appropriate Fine and Gray models will be considered.

The exploratory objectives will be tested as applicable, with two-sided tests and with a type I error rate of 0.05. No attempt will be made to adjust for multiple comparisons within the exploratory objectives.

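### SAP 7.8 analyses exploratory binary outcomes without requiring the randomization strata, and relies on an odds ratio for deaths that fails if an arm has none: a free improvement, not a validity error

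*SAP*

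**What the plan says.** SAP 2.2.4 randomizes "using a permuted block design with random block sizes and stratified by site and homelessness status". SAP 2.2.1 plans about 150 participants at three sites, "in a 1:1 ratio to either TAU or PILOT over 12 months of recruitment".

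SAP 7.8 treats the exploratory binary outcomes as follows.

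- Item 1 (each Cascade step as yes/no): "A separate logistic regression model will be fit to each with at least a treatment covariate".
- Items 2 and 5 (MOUD initiation in the ED; attendance), and item 7 for non-fatal overdose: "The effect of PILOT as compared to TAU will be measured by an OR with 95% confidence interval. A Chi-squared test will be performed".
- Item 7 for deaths: "The same process will be done for all-cause mortality and death by overdose".
- Error rate: "The exploratory objectives will be tested as applicable, with two-sided tests and with a type I error rate of 0.05", with no multiplicity adjustment.

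The section also reserves the right to use other methods. If dropout is likely it offers Kaplan-Meier and log-rank analysis, with Cox and Fine-Gray models to be considered. None of these is described as stratified. Protocol 14.8 has essentially the same text.

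Elsewhere the strata are used. The primary model (SAP 7.2) and the Cascade-count model (SAP 7.5.1) both contain site and stratum. Items 3 and 4 of SAP 7.8 call for a test like the primary one.

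**The concern.** When treatment is blocked within site and homelessness, the two arms are nearly balanced on both factors by design. A plain two-by-two test does not know this. It counts between-stratum variation in the outcome as noise, although blocking has removed most of that variation from the treatment comparison. The nominal error rate is then not fully used, and some power is lost.

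Death raises a separate question. With few events an arm may have none, and an odds ratio then has no usable value. SAP 7.8 names no other effect measure for that case.

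The stakes are modest but real. Milestone 3 (Protocol 7.4) uses repeat overdose, mortality and MOUD initiation to help size a larger trial. SAP Table 1 assigns Section 7.8 to the Lead Node, while the Data and Statistics Center runs the primary and secondary analyses, so explicit wording is useful.

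**Working it through.** **The plan's own figures.** The documents give no power, event count or expected deaths for these outcomes. The only power figures concern the primary outcome. Simulating the plan's Poisson model at baseline mean 3.55, rate ratio 0.72 and N=150 gave 93.6% against the stated 93.32%.

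**Inputs.** N = 150 at 1:1, so 75 per arm. Strata: 3 sites × 2 housing categories = 6, averaging 150/6 = 25 participants. One-year mortality 5.5% to 10% and an overdose share of 67% (Protocol 4.1). Overdose death 1.6% in the FORCE program (Protocol 4.2). Deaths are counted to Day 210. The stratum-specific event rates below are assumptions, because the documents give none.

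**Step 1: why the crude test is conservative.** Under the null, the crude variance uses p(1−p) at the pooled rate. After blocking, the true variance is close to the mean of p(1−p) within strata. By site alone:

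- Rates 25/50/75%: pooled 0.50 × 0.50 = 0.25. Within: (0.1875 + 0.25 + 0.1875)/3 = 0.2083. Ratio 0.833, square root 0.913. Actual size ≈ 2[1 − Φ(1.96/0.913)] = 2[1 − Φ(2.147)] ≈ 3.2%.
- Rates 35/50/65%: within (0.2275 + 0.25 + 0.2275)/3 = 0.235. Ratio 0.94, square root 0.970. Actual size ≈ 2[1 − Φ(2.022)] ≈ 4.3%.

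**Step 2: simulation of the crude chi-squared test against CMH.** With a_k the events on PILOT in stratum k, m_k the events in the stratum, n_1k and n_0k the arm sizes and N_k their sum,

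CMH z = Σ(a_k − n_1k·m_k/N_k) / √Σ[n_1k·n_0k·m_k(N_k − m_k) / (N_k²(N_k − 1))].

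| Assumed event rates | Size, crude | Size, CMH | Power at OR 2.5, crude | Power, CMH |
|---|---|---|---|---|
| 50% in all six strata | 4.65% | 4.55% | 77.4% | 77.4% |
| 35% to 65% over six strata | 4.6% | 4.9% | 75.1% | 76.1% |
| Sites 35/50/65% | not reported | not reported | 75.1% | 76.9% |
| Sites 25/50/75% | 3.2% | 5.2% | 64.6% | 70.4% |
| 15% to 85% over six strata | 3.0% | 5.1% | 57.2% | 68.0% |

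The six-stratum rows use equal strata of 25 and 8,000 replicates. The site rows use 50 per site, 35% homeless, a homelessness log-odds of −0.5, blocks of 4 and 6,000 replicates. An independent repeat of the site rows gave power of 65% against 71% (size 3.4% against 4.7%) and of 74% against 75%.

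**Step 3: the interval.** In the site-based setting under the null (1,500 replicates), the mean standard error of the log odds ratio was 0.329 crude and 0.369 adjusted at 25/50/75%, and 0.330 and 0.347 at 35/50/65%. Adjustment enlarges it. The power gain arises because the conditional odds ratio lies further from 1.

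**Step 4: expected deaths per arm.** 210-day risk = p × 210/365, or 1 − (1 − p)^(210/365).

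- 5.5% a year: 3.16% to 3.20%; × 75 = 2.4 deaths; × 0.67 = 1.6 overdose deaths.
- 10% a year: 5.75% to 5.88%; × 75 = 4.3 to 4.4 deaths; × 0.67 = 2.9 to 3.0 overdose deaths.
- FORCE, 1.6% taken as the 210-day risk: 75 × 0.016 = 1.2 overdose deaths.
- Upper limit, with the whole one-year 10% falling within 210 days: 7.5 deaths and 5.0 overdose deaths.

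**Step 5: chance that at least one arm has no deaths**, 1 − [1 − (1 − p)^75]².

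- All-cause: p = 3.20% gives 17%; p = 5.88% gives 2%.
- Overdose: p = 2.12% gives 36%; p = 3.94% gives 10%; p = 1.6% gives 51%.

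**Step 6: does the chi-squared test hold its level with so few deaths?** Exact enumeration at 75 per arm:

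| Death risk | Chi-squared size | Fisher size |
|---|---|---|
| 1.6% | 2.0% | 0.08% |
| 3.16% | 4.4% | 0.7% |
| 5.75% | 5.0% | 1.7% |
| 10% | 5.1% | 2.7% |

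**The case against.** The strongest reply is that little is at risk. These are exploratory outcomes in a pilot, SAP 7.8 lets the methods change, and time-to-event alternatives are already listed. The models that carry the trial's main comparisons adjust for site and stratum. The crude odds ratio is a legitimate summary, and the power gain depends on stratum differences that no document supplies. All of this stands, and it sets the severity. It does not make the unstratified test the better default: CMH held its level in every setting and matched the crude test's power when the strata did not matter.

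Four stronger readings are tempting and should be resisted.

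- A reader might infer that the item 1 models contain treatment alone. The text sets treatment as a minimum and leaves other covariates open. The gap is that site and homelessness are not required.
- A reader might infer that stratifying will narrow the intervals. Step 3 shows the opposite on the log odds ratio scale.
- A reader might infer that sparse deaths make the chi-squared test invalid and that Fisher's exact test is needed. Step 6 shows no material excess of false positives, while Fisher's test is much more conservative in a comparison whose power to detect a halving of all-cause death is only 9% to 14%.
- A reader might take expected deaths below 5 per arm as a figure from the plan. It is an inference from pro-rata scaling. Protocol 4.1 puts the highest risk in the first month, so the counts could be higher. All-cause deaths reach 5 per arm at a 210-day risk of 5/75 = 6.7%.

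**Conclusion.** The point holds as a free improvement of minor weight. SAP 7.8 does not carry the randomization strata into the tests for items 2, 5 and 7, nor require them in item 1, although the primary and Cascade-count models use them. The consequence is a conservative test, not false positives. Power lost at an odds ratio of 2.5 is about 6 points if site rates are as far apart as 25/50/75%, 1 to 2 points at 35/50/65%, and nothing without stratum differences. These sizes assume N=150. Item 2 is limited to participants with OUD, so its power will be lower than the table shows.

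For deaths, the weakness is the effect measure, not the test. Under pro-rata scaling the chance of an arm with no deaths is 2% to 17% for all-cause death and 10% to 36% for overdose death, and it falls if risk is front-loaded. The primary analysis, the Cascade-count analysis and the sample size are untouched.

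**What to change.** Amend SAP 7.8 as follows.

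1. Items 2 and 5, and non-fatal overdose in item 7: replace the plain chi-squared test with a Cochran-Mantel-Haenszel test stratified by site and homelessness, and report the matching common odds ratio with its 95% interval.
2. Item 1: require site and homelessness alongside treatment in each logistic model.
3. Item 7: if the log-rank or Cox analyses are used, stratify them by the same two factors.
4. All-cause and overdose death: report a risk difference with a score confidence interval, alongside or instead of the odds ratio. No exact test need be imposed.
5. State that the stratified or adjusted odds ratios are conditional on site and homelessness, and that their standard error on the log scale is larger than the crude one.

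The cost is SAP wording only, with no new data and no change to sample size. Protocol 14.8 already allows other methods for these objectives, so the change does not conflict with it. The trade-offs are an odds ratio that is not directly comparable with a crude one, and three extra model parameters (two for site, one for homelessness), which a rarely achieved step may strain. The counts and percentages by arm that the plan already reports remain available for planning the next trial.

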## 7.9 Missing Data Analysis

The prespecified primary outcome analysis method takes into account all available data for a participant, thereby minimizing the impact of missing values. Nevertheless, this analysis assumes that missing values are missing at random (MAR); a series of sensitivity analyses will be done to assess this assumption and the impact of missing data on the results of the primary outcome analysis.

Following standard guidance (European Medicines Agency, 2011; NIH, 2016), rates and patterns (e.g., dropout versus intermittent) of missing ORBC scores and reasons for missingness (V07 form) will be summarized by treatment arm and site to assess possible missing data mechanisms. Probability of missingness will be assessed in relation to other variables, including age, ethnicity, race, education level, marital status, employment status, and homelessness, using logistic regression. Template SAS code for examining patterns of missingness is given below:

```
proc mi data = data_miss n impute = 0;
  var day30 - day180 trt site;
  ods output miss_pattern = pattern;
run;
```

where:

- *data\_miss* is the dataset with ORCB scores (or missing values) for each treatment period visit, arranged in wide format with one row per participant,
- *day30 – day180* are the variables indicating ORBC total scores (or missing values) at Day 30, Day 90, and Day 180,
- *trt* is a treatment indicator with a value of 1 indicating PILOT and 0 indicating TAU, and
- *site* is the variable corresponding to the participant's site level.

Mechanisms of missingness cannot be concluded from observed data alone (i.e., the similarity of missing and observed values can never be evaluated). However, sensitivity analyses will be done to compare different assumptions of missingness in order to assess the robustness of conclusions from the primary outcome analysis. Considering the possibility that ORBC values may be missing not at random (MNAR), multiple imputation utilizing pattern mixture models will be performed (Ratitch, 2013). Under this approach, missing values are imputed using plausible scenarios of MNAR and, if resulting in different conclusions from MAR, may suggest that the MAR assumption of the primary outcome analysis is not robust. Multiple imputation will be performed in SAS using

Proc MI (Yuan, 2011). Imputation under the MNAR assumption will consider scenarios of missing values that have a systematically poorer outcome compared to non-missing values in the PILOT treatment arm. This analysis will quantify how much poorer (i.e., higher average ORBC total scores) missing values would need to be in order to qualitatively change the conclusions of the primary outcome analysis.

By definition, the secondary outcome measure number of steps achieved on the modified SUD Cascade of Care will have no missing data. A step is only considered attained if sufficient information is gathered by the assessment battery to meet the criteria for achievement (section 7.4.1), otherwise the step is considered not attained. No missing data handling methods are planned for the other secondary and exploratory outcomes.

## **8.0 SAFETY OUTCOMES AND ANALYSIS**

Safety outcomes include hospitalizations, ED visits, non-fatal overdoses, and suicidal ideation, and death.

### **8.1 Hospitalizations**

Treatment period and follow-up period hospitalizations will be summarized by treatment arm. The number of participants with at least one hospitalization, number of participants with at least one hospitalization related to substance use, and number of hospitalizations per participant will be presented by treatment arm. A listing of hospitalizations by treatment arm will be generated. The listing will include Site, Participant ID, date of enrollment, date of hospitalization, discharge date, primary, secondary, and tertiary diagnosis/complaint, severity, and outcome. Hospitalizations are captured on the ED Visits and Hospitalization (EDH) form.

### **8.2 Emergency Department Visits**

Treatment period and follow-up period ED visits will be summarized by treatment arm. The number of participants with at least one ED visit, number of participants with at least one ED visit related to substance use, and number of ED visits per participant will be presented by treatment arm. A listing of ED visits by treatment arm will be generated. The listing will include Site, Participant ID, date of enrollment, date of ED visit, discharge date, primary, secondary, and tertiary diagnosis/complaint, severity, and outcome. ED visits are captured on the ED Visits and Hospitalization (EDH) form.

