## 3.3 Table, Figures and Listings Conventions

Data for preliminary screened and screened populations will be summarized by site. All analyses described in the SAP for the ITT population will be summarized by randomized treatment arm (PILOT or TAU) and overall (total).

The primary outcome will be summarized by site and randomized treatment arm (PILOT or TAU). Analyses for the safety population will be summarized by randomized treatment arm (PILOT or TAU). Data quality (e.g., data audits and protocol deviations) will be summarized by site.

Continuous variables will be summarized using the following descriptive statistics: n (non-missing sample size), mean, standard deviation, percentiles (median, 25th and 75th percentiles, maximum and minimum). Categorical variables will be summarized in terms of frequencies and/or percentages.

Any deviations from the above general conventions will be noted in the subsequent subsections.

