### 17.1.8 Safety Outcomes

**Table 39: Summary of Hospitalizations by Treatment Arm**

		Treatment Arm		
Study Period 		TAU (N=XX)	PILOT (N=XX)	Total (N=XX)
Treatment Period	Number of participants with at least one hospitalization 	N (X.x%)		
	Number of participants with at least one hospitalization related to substance use 	N( X.x%)		
	Related to overdose 			
	Related to withdrawal 			
	Related to intoxication 			
	Number of hospitalizations	N	N	N
	Number of hospitalizations per participant 			
	0			
	1			
	2			
Follow-up Period	3			
	4			
	5 or more			
	Number of participants with at least one hospitalization 			
	Number of participants with at least one hospitalization related to substance use 			
	Related to overdose 			
	Related to withdrawal 			
	Related to intoxication 			
	Number of hospitalizations			
	Number of hospitalizations per participant 			
	0			
	1			
	2			
	3			
	4			
	5 or more			

Hospitalizations are as captured on the ED Visits and Hospitalization (EDH) form.

The treatment period extends from day of randomization to Study Day 180. After that, the follow-up day extends to Study Day 210.

The percentage is calculated with the denominator as the number of participants randomized.

The percentage is calculated with the denominator as the number of participants with at least one hospitalization.

The percentage is calculated with the denominator as the number of participants with at least one hospitalization related to substance use.

The hospitalization related to substance use may be due to multiple reasons.

Listing 1: Hospitalizations by Treatment Arm								
Treatment Arm = TAU								
Site	Participant ID	Date of Randomization	Hospitalization Date	Discharge Date	Primary Diagnosis/Complaint	Secondary Diagnosis/Complaint	Tertiary Diagnosis/Complaint	Outcome
xxxxx	xxxxxxxxxxxx	mm/dd/yyyy	mm/dd/yyyy	mm/dd/yyyy	xxxxxxxx	xxxxxxxx	xxxxxxxx	Recovering/resolving Recovered/resolved Recovered/ resolved with sequelae Not recovered/not resolved Fatal Unknown

Listing 1: Hospitalizations by Treatment Arm								
Treatment Arm = PILOT								

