**Table 40: Summary of ED Visits by Treatment Arm**

		Treatment Arm		
Study Period 		TAU (N=XX)	PILOT (N=XX)	Total (N=XX)
Treatment Period	Number of participants with at least one ED visit 	N (X.x%)		
	Number of participants with at least one ED visit related to substance use 			
	Related to overdose 			
	Related to withdrawal 			
	Related to intoxication 			
	Number of ED visits			
	Number of ED visits per participant 			
	0			
	1			
	2			
	3			
	4			
	5 or more			
Follow-up Period	Number of participants with at least one ED visit 			
	Number of participants with at least one ED visit related to substance use 			
	Related to overdose 			
	Related to withdrawal 			
	Related to intoxication 			
	Number of ED visits			
	Number of ED visits per participant 			
	0			
	1			
	2			
	3			
	4			
	5 or more			

ED Visits are as captured on the ED Visits and Hospitalization (EDH) form and do not include the index ED visit.

The treatment period extends from day of randomization to Study Day 180. After that, the follow-up day extends to Study Day 210.

The percentage is calculated with the denominator as the number of participants randomized.

The percentage is calculated with the denominator as the number of participants with at least one ED visit.

The percentage is calculated with the denominator as the number of participants with at least one ED visit related to substance use.

The ED visit related to substance use may be due to multiple reasons.

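### In the SAP shells for Tables 39 and 40, the substance-related and overdose-related percentages are taken among participants who had an event, so they are not arm risks and can differ in direction from the risks per participant randomized

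*SAP*

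**What the plan says.** SAP 8.1 and 8.2 list three summaries by arm: participants with any event, participants with a substance-related event, and events per participant. For hospitalizations the second is the "number of participants with at least one hospitalization related to substance use"; for ED visits the text reads "number of participants with at least one ED visit related to substance use, and number of ED visits per participant will be presented". No denominator appears in either section. SAP 3.3 sets the comparison: "Analyses for the safety population will be summarized by randomized treatment arm (PILOT or TAU").

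The denominators are in the footnotes to the shells in the SAP appendix (Safety Outcomes, Tables 39 and 40):

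- Any event, and events per participant (footnote 2): "The percentage is calculated with the denominator as the number of participants randomized". Table 40 has the same rule.
- Substance-related event (footnote 3): "The percentage is calculated with the denominator as the number of participants with at least one hospitalization" in Table 39, and "The percentage is calculated with the denominator as the number of participants with at least one ED visit" in Table 40.
- Related to overdose, withdrawal or intoxication (footnote 4): "The percentage is calculated with the denominator as the number of participants with at least one hospitalization related to substance use" in Table 39, and "The percentage is calculated with the denominator as the number of participants with at least one ED visit related to substance use" in Table 40.

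The same footnotes serve the treatment and follow-up periods. The shells plan counts with percentages under column headers that carry the arm N. No row gives substance-related or overdose-related events as a percentage of those randomized. Protocol 14.11 asks only for tabular summaries of the targeted safety events and sets no denominator.

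**The concern.** Three adjacent kinds of row under one arm header use three different denominators. Only the first is fixed at randomization. The number of participants with any ED visit or hospitalization, and the number with a substance-related one, are outcomes that PILOT could itself alter. A percentage taken within such a group describes the mix of events among those who had one. It does not give the risk in the arm, and randomization does not protect its comparison between arms.

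SAP 8.1 and 8.2 name the substance-related row as a safety outcome to be presented by arm, so readers will compare the two arm columns. If PILOT lowers the risk of any event proportionally more than the risk of a substance-related event, the printed percentage is higher for PILOT even though fewer PILOT participants had a substance-related event. The same can happen one level down, in the overdose rows.

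**Working it through.** There is no figure in the plan to reproduce. The check is algebra followed by arithmetic.

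**Inputs.** About 150 participants randomized 1:1 (SAP 2.2.1), so n = 150/2 = 75 per arm. Denominators are from footnotes 2 to 4. The documents give no planning rates for these events by arm, so every count below is an assumption.

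**Formulas.** In each arm let A, S and O be the numbers of participants with any event, a substance-related event and an overdose-related event.

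- Footnote 2 prints A/n, footnote 3 prints S/A, and footnote 4 prints O/S.
- With RR the PILOT to TAU ratio of risks per participant randomized, the ratio of the footnote 3 percentages is RR(S)/RR(A), and the ratio of the footnote 4 percentages is RR(O)/RR(S).
- So, when PILOT has the lower risk, the substance-related row reverses if RR(A) < RR(S) < 1, and the overdose row reverses if RR(S) < RR(O) < 1.

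**Example 1, hospitalizations.** PILOT: A = 6, S = 4, O = 3. TAU: 15, 8, 6.

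- Substance-related as specified: 4/6 = 66.7% PILOT, 8/15 = 53.3% TAU. Of those randomized: 4/75 = 5.3% and 8/75 = 10.7%.
- Check: RR(A) = 6/15 = 0.40 and RR(S) = 4/8 = 0.50, so the printed ratio is 0.50/0.40 = 1.25 although the risk is halved.
- Overdose-related as specified: 3/4 = 75% and 6/8 = 75%. Of those randomized: 3/75 = 4.0% and 6/75 = 8.0%. This row ties; it does not reverse.

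**Further assumed sets** (75 per arm; each cell is TAU vs PILOT):

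| A/S/O, TAU vs PILOT | S/A as specified | S/75 | O/S as specified | O/75 |
|---|---|---|---|---|
| 40/24/12 vs 24/18/10 | 60.0% vs 75.0% | 32.0% vs 24.0% | 50.0% vs 55.6% | 16.0% vs 13.3% |
| 30/18/9 vs 20/14/8 | 60.0% vs 70.0% | 24.0% vs 18.7% | 50.0% vs 57.1% | 12.0% vs 10.7% |
| 50/25/15 vs 30/18/12 | 50.0% vs 60.0% | 33.3% vs 24.0% | 60.0% vs 66.7% | 20.0% vs 16.0% |
| 30/18/9 vs 30/14/7 | 60.0% vs 46.7% | 24.0% vs 18.7% | 50.0% vs 50.0% | 12.0% vs 9.3% |

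Both rows reverse in the first three sets. In the fourth, where the arms have equal numbers with any event, neither reverses; the overdose row ties.

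**How often the signs differ.** Binomial simulation of the substance-related row: 100,000 runs per setting, 75 per arm, assumed TAU any-event risk 30%, 50% or 70%, assumed substance-related share in TAU 40% or 60%. The table gives the share of runs in which the difference in S/A and the difference in S/75 have opposite signs.

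| RR(A), RR(S) | Opposite signs |
|---|---|
| 1, 1 | 9.8% to 21.2% |
| 0.8, 0.8 | 19.0% to 34.5% |
| 0.7, 0.8 | 28.8% to 63.6% |
| 0.6, 0.75 | 39.9% to 81.9% |

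The first line is chance alone. The last two are settings where PILOT lowers any-event risk more than substance-related risk.

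**The case against.** The strongest reply is that nothing is hidden. Cells show a count beside each percentage, the arm N stands above, allocation is 1:1, and each denominator is footnoted. In Example 1 the table would print 4 (66.7%) against 8 (53.3%), and the halving is visible in the counts. This stands. A reader might infer that the arms cannot be compared on these events at all. They can, from the counts and N; only the printed percentages mislead.

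Second, nested denominators are this SAP's habit for breakdowns, such as reasons for ineligibility (Table 1), early termination (Tables 5, 6 and 18) and missed visits (Tables 11 and 12). The type of event among those who had one is a fair description, so the conditional share may be kept. But the substance-related row is a named outcome by arm in SAP 8.1 and 8.2, and no row gives its risk.

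Third, overdose is reported elsewhere. SAP 8.3 and Table 41 count participants with an opioid overdose by arm and visit from the overdose information form. Exploratory Aim 7 (SAP 7.7 and 7.8) compares non-fatal overdose and death with odds ratios and chi-squared tests. So a reader who took Tables 39 and 40 for the trial's main or only overdose evidence would be mistaken. Table 41 is still no substitute for these rows: its ED-treated and hospital-admitted lines count overdoses among the two most recent per participant per visit, not participants with an overdose-related visit.

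Fourth, the counts are invented and some were chosen to reverse. That is true, and the size below is conditional on them.

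**Conclusion.** The point holds as a flaw of descriptive presentation. The percentages under footnotes 3 and 4 are conditional on post-randomization events, are not arm risks, and can point the opposite way from the risks per participant randomized. In Example 1 the substance-related row is 66.7% PILOT against 53.3% TAU as specified, and 5.3% against 10.7% of those randomized. Direction and size depend on event rates that the documents do not give. For the substance-related row to reverse, the arms must differ in the proportion with any event.

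Two stronger readings are not supported. A reader might infer that the DSMB would be misled. SAP 11.1 describes descriptive safety looks for the DSMB but does not say that they use these shells, and SAP 1.0 places the SAP's analyses after data lock. A reader might also infer that a trial conclusion is at risk. No test or decision rule uses these rows, and the primary analysis does not depend on them. The sentences in SAP 8.1 and 8.2 are not wrong in themselves: they promise numbers of participants, which the tables deliver. The defect lies in the table footnotes.

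**What to change.** In Tables 39 and 40, change footnotes 3 and 4 so that the substance-related, overdose, withdrawal and intoxication rows use the number of participants randomized to the arm, as footnote 2 does for any event. Apply this to both the treatment and follow-up periods. If the share among participants with an event is wanted, print it as a separate figure labelled as conditional. State the denominator in SAP 8.1 and 8.2.

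The cost is two footnotes in each table, a sentence in each of the two SAP sections and a small change to the table program. No new data are needed.
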